This study will enroll up to 86 subjects in total, with 14 subjects in the Phase I portion and up to 72 subjects with a 1:1 randomization ratio to either CYNK-001 or the best supportive care control arm as defined by the institutional practice in the Phase II portion of the study.

Investigational product, dosage and mode of administration:

CYNK-001 dosage and mode of administration:

Dose Level 1: CYNK-001 with an initial Dose of 150×10^6 cells on Day 1 followed by 600×10^6 cells on Days 4 and 7 (second and third doses). After the first dose, subsequent infusions on Days 4 and 7 will be provided only if no toxicity of Grade 3 and above (either related or unrelated to CYNK-001) is observed for each subject. If any such \geq Grade 3 toxicity is observed, the second and third doses will be delayed up to 48 hours until the noted event is resolved or reduced to Grade 1 toxicity level.

Dose de-escalation Level -1: Dose de-escalation is defined as reducing the frequency of the doses (without reducing the total number of cells given per dose) by providing doses only on Days 1 and 7 for any potential safety concerns per DMC recommendation. CYNK-001 with an initial dose of 150×10^6 cells on Day 1 followed by 600×10^6 cells on Day 7.

CYNK-001 is to be administered IV using a gravity IV administration set with a 16- to 22- gauge (or equivalent) needle or catheter with no filters. A central line may be used to infuse CYNK-001 after confirming that the catheter diameter is 16- to 22- gauge (or equivalent) needle. For substantial deviation from this catheter diameter consultation with the medical monitor is required. The recommended infusion rate is approximately 240 mL per hour.

Subjects will receive pre- and post- medication of acetaminophen (650mg PO) and diphenhydramine (25mg PO/IV) at least 30 minutes prior to and approximately 4 hours after each CYNK-001 infusion.

Vital signs will be taken prior to, approximately 30 minutes after the start, and approximately 4 hours after the completion of each infusion. Subjects must be monitored for at least 4 hours after completion of each CYNK-001 infusion.

Dose Modifications

Dose adjustments may occur if clinically indicated by the treating physician. In general, the following should be followed:

- Dose reductions are not permitted in this study. If DLTs safety concerns are observed, the dose de-escalation treatment with reducing frequency of doses will be implemented per DMC recommendation.

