12.1.4. Vital Signs

Vital signs will be measured, including temperature, systolic and diastolic blood pressure, respiration rate, and pulse and oxygen saturation (SpO₂), per standard institutional practice as outlined in the Table of Events.

Vital signs to be collected from medical record during hospitalization. Once subject is discharged the vital signs should be collected in the outpatient facility where the subject is seen.

Upon discharge, plans should be made for appropriately delegated study staff to have telephone contact with subjects every day between hospital discharge through at least Day 15 visit for safety/AE monitoring. Subjects will be provided with a thermometer, pulse oximeter, and blood pressure monitor for at home collection of temperature, oxygen saturation, and blood pressure with written instructions on their use as well as expectations for self-monitoring. These daily measurements will be reported via telephone to the clinical staff during each daily telehealth visit. During these daily telehealth visits, subjects are to report any new symptoms or worsening of symptoms associated with previously identified adverse events and will also provide the study team with daily vital sign measurements. Any vital signs outside of normal range will be escalated to the clinical site study team and evaluated for appropriate management. The subject will be asked during each call to report any new or worsening symptoms that could be consistent with adverse events since the previous visit or telephone call. The investigator (or appropriately delegated study staff) will determine if medical attention or an unscheduled clinic visit is required. Each telephone call should be carefully documented with date and time of the call in the source documents and reported as appropriate.

On each day of CYNK-001 infusion, vital signs to be collected pre-infusion, approximately 30 minutes after the start of infusion, and approximately 4 hours after the completion of infusion.

On non-infusion days where multiple vital signs are collected throughout the day, vital signs should be captured in the EDC once per day and the worst vitals should be recorded.

Note: Subjects must be monitored for at least 4 hours after completion of each CYNK-001 infusion.

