2.1 Primary Objective

Phase I Study

The primary objectives of the Phase I portion of the study are to evaluate the safety, tolerability, and efficacy of multiple CYNK-001 intravenous (IV) infusions administered with an initial dose of 150×10^6 cells on Day 1 followed by 600×10^6 cells on Days 4 and 7 in subjects with COVID-19.

Phase II Study

The primary objective of the phase II portion is to evaluate the efficacy of CYNK-001 on subjects with COVID-19 by using the Ordinal Scale for Clinical Improvement (OSCI) defined by the World Health Organization (WHO).

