14.3 Vital signs

Vital signs and the changes from baseline will be summarized descriptively with mean, standard deviation, median, range and 95% confidence interval by infusion time point at Day 1, Day 4 and Day 7. The clinically significant status of vital signs will also be tabulated. During the infusion day, the summary of vital signs will be summarized separately by infusion time point as pre-infusion, 30 minutes post-infusion and 4-hours post infusion.

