14.7 Infectious Symptom Assessment

The infectious symptom assessment will be tabulated over time with the proportion of clinical status assessment as defined in the CRF. The descriptive statistics, including the proportion and its 95% confidence interval will be provided.

No missing data will be imputed for this part of analysis nor formal hypothesis testing will be performed.

Subject level listing of AEs, vital signs, laboratory assessments and inflammation assessments will be provided.

15. Changes in Conduct or Planned Analyses from the Protocol

Description of change of conduct: Early termination of the study by the company.

In review of the current status and enrolment challenges of the CYNK-001-COVID-19 clinical trial and given the current landscape of the COVID-19 pandemic and the rollout COVID-19 vaccine, a decision by

Celularity has been made to close the CYNK-001-COVID-19 clinical trial. As a result of this early termination, only 7 patients were enrolled and dosed in the Phase I portion.

Due to this change, a brief clinical study report will be provided instead of a full CSR. Based on this change, only the following analysis will be provided for Phase I along with supporting listings:

- Summary of Subject disposition
- Summary of major protocol deviations
- Summary of demographics and baseline characteristics
- Analysis of time to clinical improvement by NEWS2 score
- Analysis of rRT-PCR tests and time to clearance of SARS-CoV-2 by rRT-PCR results (if enough data available)
- Analysis of SOFA scores (if enough data available)
- Summaries of adverse events
- List of deaths
- Summaries of laboratory results, shift from baseline and abnormal laboratory values
- Summaries of vitals signs, oxygen saturation and ECG and shifts from baseline
- Summary of abnormal post-baseline QTc results

16. Analysis of Concomitant Medication and Concomitant Procedure

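### SAP 14.3 labels a reading timed from the start of infusion as post-infusion, leaves baseline undefined for vital signs, and plans no change from the same-day pre-infusion reading

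*SAP*

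**What the plan says.** SAP 14.3 states: "Vital signs and the changes from baseline will be summarized descriptively with mean, standard deviation, median, range and 95% confidence interval". This applies to each timed reading on Days 1, 4 and 7. On infusion days the results are to be "summarized separately by infusion time point as pre-infusion, 30 minutes post-infusion and 4-hours post infusion". The section also tabulates clinically significant status. It does not define baseline and names no change from the pre-infusion reading of the same day.

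The protocol gives the collection times twice. Section 12.1.4 has "vital signs to be collected pre-infusion, approximately 30 minutes after the start of infusion, and approximately 4 hours after the completion of infusion". The synopsis agrees: "Vital signs will be taken prior to, approximately 30 minutes after the start, and approximately 4 hours after the completion of each infusion".

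Three other places bear on the point:

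- Changes in vital signs are a named part of the Phase I primary safety endpoint (protocol Table 2; SAP Study Summary).
- SAP 15, written after the decision to close the trial with 7 subjects dosed, retains "Summaries of vitals signs, oxygen saturation and ECG and shifts from baseline".
- SAP 4.7 sets a general rule for safety summaries: use the last observation of the study day.

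**The concern.** There are two separate problems.

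**Label.** One SAP sentence applies the term post-infusion to two readings with different time origins: the start for the middle one, completion for the last. A reader of the table would take the middle reading as a value after exposure had ended. Depending on the infusion volume, it may have been taken while cells were still running in.

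**Reference value.** The question that infusion-day readings can answer best is what happened between just before and shortly after the infusion. A change from a study-level baseline does not isolate that on Days 4 and 7. It adds whatever happened to the illness in between. Improvement would make the change column understate a rise, and deterioration would make it look like one. With 7 subjects, the spread of the within-day change matters most, because it shows whether a single subject reacted. The planned tables do not give it.

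**Working it through.** No design figure of the plan is involved, so there is none to reproduce. The check sets the texts side by side and follows the arithmetic.

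**1. Time points**

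| Reading | Protocol (synopsis, 12.1.4) | SAP 14.3 label |
|---|---|---|
| First | before infusion | pre-infusion |
| Second | about 30 min after the start | 30 min post-infusion |
| Third | about 4 h after completion | 4 h post infusion |

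Only the second row conflicts. The conflict applies to Day 1 as much as to Days 4 and 7.

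**2. Size of the labelling error.** The synopsis says: "The recommended infusion rate is approximately 240 mL per hour". So 30 minutes delivers 240 × 0.5 = 120 mL. The total volume is not in the readable text, so a range is assumed. Duration T = volume / 240 × 60 minutes.

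| Assumed volume | T | Second reading relative to end of infusion |
|---|---|---|
| 60 mL | 15 min | 15 min after |
| 120 mL | 30 min | at the end |
| 240 mL | 60 min | 30 min before |
| 480 mL | 120 min | 90 min before |

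If the label is read as 30 minutes after completion, it points to T + 30 minutes after the start. The reading is taken at 30 minutes, so the label is off by T: 15 to 120 minutes over this range.

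**3. What baseline means.** The SAP does not say. Three things point to one study-level value. Protocol 12.1.6 pairs baseline with screening. The oxygen rule in protocol 6.5 separates baseline from the level at a prior infusion. And if baseline were the same-day pre-infusion reading, the change at the pre-infusion time point would always be zero. This is an inference, not a stated definition. A further reason to settle it is that protocol 12.1.4 records the worst vital signs of the day on non-infusion days with several readings. A baseline from a separate screening day could then be a worst-of-day value, which would tilt changes towards apparent improvement.

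**4. What the change column contains.** For each subject:

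post − baseline = (same-day pre − baseline) + (post − same-day pre).

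Illustration, all inputs assumed: an acute heart-rate rise of 10 bpm and a recovery drift since baseline of 0, −5, −10 or −15 bpm. The mean 30-minute change from baseline is then +10, +5, 0 or −5 bpm. The within-day change is +10 in every case.

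**5. What can be recovered from the planned tables.** For the same subjects with complete data,

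mean(post − baseline) − mean(pre − baseline) = mean(post − pre).

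The identity is exact; simulated data at n = 7 and n = 14 gave identical values on both sides. So the mean is recoverable.

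The SD is not. SD(post − pre) = SD × √(2(1 − r)), where r is the pre–post correlation, which no planned table gives. Assume SD 12 bpm and a correlation of 0.5 of each reading with baseline. These allow r anywhere within 0.5 × 0.5 ± (1 − 0.5²), that is −0.5 to 1. SD(post − pre) could then lie between 0 and 12 × √3 = 20.8 bpm.

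**6. Precision, for scale (assumed SD 12 bpm).**

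- Change from baseline, correlation 0.3, 0.5 or 0.7: SD 14.2, 12.0 or 9.3 bpm.
- Within-day change, correlation 0.8: 12 × √0.4 = 7.6 bpm.
- 95% CI half-width at n = 7 (t = 2.447): 2.447 × 12.0 / √7 = 11.1 bpm against 2.447 × 7.6 / √7 = 7.0 bpm.

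**7. Rule conflict.** On an infusion day the last observation would normally be the 4-hour reading. Applied literally, SAP 4.7 would keep that one and drop the other two, which 14.3 wants shown. Neither section says which governs.

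**The case against.** The strongest case against is that little is lost. The pre-infusion reading is its own time point. In the illustration with a drift of −10, Day 7 would show about −10 before the infusion and 0 at 30 minutes, so the rise is visible. Listings of individual vital signs are planned (SAP 14.7), and 7 subjects can be read by eye. Infusion-related reactions are documented for 72 hours at every dose (protocol 12.3.1.1). Clinically significant vital signs, CRS, Grade 3 or higher events and DLTs have their own summaries. Mean vital-sign change enters no stopping rule or DLT definition. Protocol 14.5 asks only for changes over time, which 14.3 provides. SAP 15 does not say that the by-time-point table survives the early closure. The within-day change is not a pure infusion effect either, since acetaminophen and diphenhydramine are given beforehand.

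Most of this stands and keeps the point modest. It does not remove it. Subtraction yields a mean and nothing about spread, SAP 14.1 lists no infusion-reaction table, and none of these arguments touches the label.

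A reader might infer more than the documents support:

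- *That recovery cancels an infusion reaction and hides it.* It does not; the separate pre-infusion row prevents that.
- *That the three readings were designed to make each subject their own control.* The protocol states no such purpose.
- *That the second reading is certainly mid-infusion, or that no reading exists 30 minutes after completion.* The volume and most of the Table of Events are not available here.
- *That only the larger doses are affected.* The label covers all three infusions. On Day 1 the drift is likely small, since screening may last less than a day (protocol 6.1.1).

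**Conclusion.** Two findings are firm. The SAP label for the second reading contradicts the protocol's collection time for every infusion. SAP 14.3 also leaves baseline undefined for vital signs and specifies no within-day change. The protocol's collection time itself is clear; the error lies in the SAP.

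That the change column on Days 4 and 7 mixes disease course with acute effect rests on reading baseline as one study-level value. That reading is well supported but inferred. If baseline were instead the Day 1 pre-infusion reading, Day 1 would already be a within-day change and Days 4 and 7 would be unaltered.

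The consequence is modest. These are descriptive safety summaries for 7 dosed subjects, and no hypothesis test, sample size or decision rule depends on them. The bpm and mL figures only illustrate scale and rest on stated assumptions. The correction is still worth making, because vital-sign changes belong to the Phase I primary safety endpoint and the better summary uses data already specified for collection.

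**What to change.** In SAP 14.3:

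1. Rename the second and third time points *30 minutes after start of infusion* and *4 hours after completion of infusion*.
2. Define baseline for vital signs, including which reading is used when several exist.
3. For each infusion (Days 1, 4 and 7), add the change from that day's pre-infusion reading to the 30-minute and 4-hour readings, with the same descriptive statistics. Show it beside the existing change from baseline, not in its place.
4. State that 14.3 overrides the latest-observation rule of SAP 4.7 on infusion days.

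SAP 15 should also say whether the by-time-point table is among the retained summaries.

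The cost is SAP wording and one extra programmed table. No new data are needed, and collection and clinical procedures are unchanged.

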14.4 Physical exams

Physical exams will be listed.

14.5 Immunological / Inflammation Assessments

High sensitivity C-reactive protein (CRP), ferritin, and D-dimer results and the change from baseline will be summarized over time descriptively with mean, standard deviation, median, range and 95% confidence interval.

14.6 Chest X-ray

The assessment of pulmonary infiltrate and pleural effusion over time will be tabulated separately for pre-specified age strata and overall population.

14.7 Infectious Symptom Assessment

The infectious symptom assessment will be tabulated over time with the proportion of clinical status assessment as defined in the CRF. The descriptive statistics, including the proportion and its 95% confidence interval will be provided.

No missing data will be imputed for this part of analysis nor formal hypothesis testing will be performed.

Subject level listing of AEs, vital signs, laboratory assessments and inflammation assessments will be provided.

15. Changes in Conduct or Planned Analyses from the Protocol

Description of change of conduct: Early termination of the study by the company.

In review of the current status and enrolment challenges of the CYNK-001-COVID-19 clinical trial and given the current landscape of the COVID-19 pandemic and the rollout COVID-19 vaccine, a decision by

Celularity has been made to close the CYNK-001-COVID-19 clinical trial. As a result of this early termination, only 7 patients were enrolled and dosed in the Phase I portion.

Due to this change, a brief clinical study report will be provided instead of a full CSR. Based on this change, only the following analysis will be provided for Phase I along with supporting listings:

- Summary of Subject disposition
- Summary of major protocol deviations
- Summary of demographics and baseline characteristics
- Analysis of time to clinical improvement by NEWS2 score
- Analysis of rRT-PCR tests and time to clearance of SARS-CoV-2 by rRT-PCR results (if enough data available)
- Analysis of SOFA scores (if enough data available)
- Summaries of adverse events
- List of deaths
- Summaries of laboratory results, shift from baseline and abnormal laboratory values
- Summaries of vitals signs, oxygen saturation and ECG and shifts from baseline
- Summary of abnormal post-baseline QTc results

16. Analysis of Concomitant Medication and Concomitant Procedure

